#### **Mechanism for Monitoring Patient Safety**

##### Study Oversight

The CFFT Data Safety Monitoring Board (DSMB) at the University of Arizona will provide trial oversight. A Data Monitoring Committee (DMC) a subcommittee of the DSMB will be formed for this trial in order to review the protocol, patient informed consent, and safety monitoring plan. During the study, the DMC will be responsible for real-time serious adverse event monitoring and reviewing interim safety reports to ensure the continued safety, scientific validity and merit of the trial and to make recommendations concerning continuation, termination or modification of the trial. The DMC will include at least two CF clinicians, and a biostatistician.

##### Adverse Events (AE)

An adverse event will be defined as any unfavorable and unintended sign, symptom, or disease temporally associated with the use of Revatio® or other protocol-imposed intervention, regardless of attribution.

This definition will include the following:

- AEs not previously observed in the subject that emerge during the study period, including signs or symptoms associated with CF that were not present prior to the study period
- Complications that occur as a result of protocol-mandate interventions (e.g. sputum induction)

- Preexisting medical conditions (other than the condition being studied) judged by the investigator to have worsened in severity or frequency or changed in character during the protocol-specified AE reporting period

Subjects will be questioned and/or examined by the Investigator or her designee for evidence of adverse events.

Subjects having adverse events will be monitored with relevant clinical assessments and laboratory tests as determined by the investigator. All adverse events will be followed to satisfactory resolution or stabilization of the event(s.) Any actions taken and follow-up results will be recorded on the appropriate page of the CRF, as well as in the subject's source documentation. Follow-up laboratory results will be filed with the subject's source documentation.

For all adverse events that require the subject to be discontinued from the study, relevant clinical assessments and laboratory tests will be repeated until satisfactory resolution or stabilization of the event(s.)

A serious event will be determined as follows:

- It results in death
- It is life threatening
- It requires or prolongs inpatient hospitalization (with the exception of pulmonary exacerbation unrelated to study drug, see section G)
- It results in persistent or significant disability/incapacity
- It results in a congenital anomaly/birth defect in a neonate/infant born to a mother exposed to the investigational product
- It is considered a significant medical event by the investigator based on medical judgment

Grading of AEs will be as follows:

•Mild: Transient or mild discomfort (<48 hours); no interference with the subject's daily activities; no medical intervention/therapy required

•Moderate: Mild to moderate interference with the subject's daily activities; no or minimal medical intervention/therapy required

•Severe: Considerable interference with the subject's daily activities; medical intervention/therapy required; hospitalization possible

To determine the causality of AE and SAE the follow guidelines will be assessed:

- **Definitely**: There is a plausible temporal relationship between the onset of the AE and administration of sildenafil, and the AE cannot be readily explained by the subject's clinical state, intercurrent illness, or concomitant therapies; and/or the AE abates or resolves upon discontinuation of sildenafil.
- **Probably**: There is a plausible temporal relationship between the onset of the AE and administration of sildenafil, and the AE follows a typical response to sildenafil, but a potential alternative cause may be present.
- **Unlikely**: There is a reasonable possibility that the onset of the AE is related to the administration of sildenafil, but an alternative cause seems more likely.
- **Unrelated**: Evidence exists that the AE has an etiology other than administration of sildenafil (e.g., preexisting medical condition, underlying disease, intercurrent illness, or concomitant medication); and/or the AE has no plausible temporal relationship to administration of sildenafil (e.g., cancer diagnosed 2 days after first dose of study drug.)

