*Study visit 3 (Day 7±3):* After 7 days of therapy, the subject will return to the study site for vital signs, review of concomitant medications, and discussion of concerns related to sildenafil therapy. If tolerated (see **Subject and Study Stopping Criteria**), the oral sildenafil or placebo dose will be increased to 40mg, three times daily. If there is evidence of sildenafil intolerance (blood pressure will be checked at 30 minutes, 1 hour, and 2 hours after the first increased dose), the dose will be decreased to the previous dose or discontinued. If sildenafil is

discontinued, the patient will be removed from the study. Oral sildenafil therapy will continue at 40mg, three times daily for eleven weeks. (Total sildenafil or placebo therapy will last twelve weeks.)

*Phone contact 1 (Day 28±3):* Phone contact will be made with each subject to review dosing, compliance and side effect profiles. Phone contacts will be recorded on case report forms.

*Study visit 4 (Day 42±3):* The subject will return to the study site for CFQ—R vital signs, review of concomitant medications, and discussion of concerns related to sildenafil therapy. A study investigator will perform a brief physical exam. The subject will perform spirometry and will complete a 6MWT.

*Study visit 5 (Day 84±3):* Subjects will return to the outpatient research unit, where the CFQ-R (see description below) will be administered prior to all other assessments. A physical exam will be performed by a study investigator. Vital signs, weight, safety labs, and urine pregnancy in all women, will be done. Spirometry will be performed. Sweat test will be performed. After completing spirometry, cardiac MRI will be performed, a six-minute walk test and cycle ergometry test will be performed (see description of each procedure below). Tests will be performed in that order. Subjects will have a 30 minute rest period between the six-minute walk and the cycle ergometry test. The fit-bit will be removed. At the conclusion of this visit, subjects will be instructed to discontinue sildenafil or placebo therapy.

*Phone contact 2 (Day 98±3):* The study coordinator will call to review adverse events and concomitant medications. If there are new abnormalities or changes in medication felt to be study-related, these abnormalities will be followed up with weekly visits to the study site until resolution.

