*Exacerbations:* During the course of the study, any enrolled subject requiring hospitalization and/or intravenous antibiotics for a cystic fibrosis-related pulmonary exacerbation will be withdrawn from the study.

*Early Withdrawal:* In case of early withdrawal, an Early Withdrawal Visit will be scheduled within 7 days following the last dose of study medication. Unless medically contraindicated, CFQR, safety labs, serum pregnancy for all women, spirometry, a six-minute walk test and cycle ergometry test will be performed. Physical exam will be performed by a study investigator including weight, temperature, blood pressure, respirations and pulse oximetry. Any abnormal findings will be documented. All remaining study drug will be collected.

*Concomitant medications:* All subjects should continue the same medications throughout the study period, as medically feasible, with no introduction of new chronic therapies during or <4 weeks prior to enrollment. If a change in concomitant medications is required, the reason(s) for the change(s) will be recorded on the subject's CRF.

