#### Known Potential Toxicity of Study Drug

In trials of sildenafil, adverse effects were generally mild to moderate and transient in nature. The overall frequency of discontinuation in Revatio® -treated patients at the recommended dose of 20 mg t.i.d. was low (3%) and the same as placebo (3%) Side effects that occurred in more than 2%, and more frequently by patients on study drug than on placebo included headache (67% vs. 56%) epistaxis (13% vs. 2%) flushing (15% vs. 6%) , dyspepsia (19% vs. 10%), nasal congestion (6% vs. 0%), insomnia (11% vs. 2%), erythema (9% vs. 2%), exacerbation of dyspnea (11% vs. 5%), diarrhea (13% vs. 9%) , myalgia (11% vs 6%), pyrexia (9% vs 5%), gastritis (5% vs 0%), sinusitis (5% vs 0%) and paresthesia (5% vs 0%.) At doses *higher than the recommended dose* of 20mg t.i.d., incidence of adverse events of some symptoms was increased including flushing, diarrhea, myalgia and visual disturbances (mild and transient color-tinge, sensitivity to light or blurred vision.) Incidence of retinal hemorrhage in subjects taking the recommended dose was 1.9% vs placebo and occurred in patients on anti-coagulation. Patients in this study will not be on anticoagulation. There was no report of priapism in the placebo controlled trial of Revatio®.

Post-marketing experience of Viagra® (dosed as 50-100 mg once daily for erectile dysfunction), has demonstrated serious cardiovascular, cerebrovascular and vascular events, as well as priapism and ischemic retinopathy. These adverse events were not seen in the randomized, placebo-controlled trial of Revatio® for pulmonary hypertension. The majority of these events occurred in patients with preexisting cardiovascular risk factors. Patients with cardiovascular risk factors will not be included in the study.

Revatio® did cause transient decreases in supine blood pressure in healthy volunteers (mean maximum decrease in systolic/diastolic blood pressure 8.4/5.5mmHg.) Subjects in this study will have monitoring of their blood pressure following administration of the initial doses of study drug (30 minutes, 60 minutes, and 120 minutes after the initial dose of 20 mg at visit 2, and subsequent to the first 40 mg dose at visit 3).

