### Medical Monitor

The medical monitor ([name]) should be contacted directly for any medical or safety concerns. The medical monitor will review all SAE. If an SAE qualifies for expedited reporting to regulatory agencies (classified as unexpected and related to study drug), the medical monitor will immediately notify [name] by phone or pager. Within one business day of medical monitor review, the SAE report will be distributed to the Data Monitoring Committee (DMC) chair.

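### Resolution on stopping drug is enough by itself for the *Definitely* related grade, so one event can fit both *Definitely* and *Unrelated*, and no rule says which prevails

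*Combined protocol and SAP*

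**What the plan says.** The causality guidelines are the list of four grades that closes the Adverse Events (AE) section.

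- *Definitely* has a first limb with two conditions: plausible timing, and that "the AE cannot be readily explained by the subject's clinical state, intercurrent illness, or concomitant therapies". After a semicolon comes a second limb: "and/or the AE abates or resolves upon discontinuation of sildenafil".
- *Probably* also needs plausible timing, and that "the AE follows a typical response to sildenafil, but a potential alternative cause may be present".
- *Unrelated* has a first limb, "Evidence exists that the AE has an etiology other than administration of sildenafil", with intercurrent illness and underlying disease among its examples. A second limb, absence of plausible timing, is joined by the same semicolon and and/or.

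No sentence says which grade applies when an event meets two definitions, and no time window is given for resolution on stopping.

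Other parts of the protocol bear on this:

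- Study Timeline, visit 5 (Day 84±3): "subjects will be instructed to discontinue sildenafil or placebo therapy". An adverse-event call follows at Day 98±3.
- Study Timeline, Exacerbations: a subject who needs hospitalization and/or intravenous antibiotics for a "cystic fibrosis-related pulmonary exacerbation will be withdrawn from the study".
- Medical Monitor: a serious event qualifies for expedited reporting when "classified as unexpected and related to study drug".
- Adverse Events (AE), seriousness criteria: hospitalization counts as serious, except for an exacerbation unrelated to study drug.
- Allocation and blinding: investigators do not know the arm.

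**The concern.** A causality scale should place each event in one grade, and its top grade should be the hardest to reach. Here the top grade has a route that asks nothing about when the event began or what else could have caused it. Many events resolve naturally, so recovery after stopping is weak evidence on its own. An event with a documented other cause, ongoing when drug is stopped, can be placed at either end of the scale by two careful graders, each following the text.

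The grade has uses beyond description. It decides whether an unexpected serious event is reported on an expedited basis and whether a hospitalized exacerbation escapes the seriousness criterion. Under phone contact 2 it also decides which late abnormalities get weekly follow-up visits. Specific Aim 2 asks whether sildenafil is safe, and with 12 to 20 subjects one or two discretionary grades could change how the safety result reads.

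**Working it through.** The plan gives no figure on this point, so there is none to reproduce. The check is logical, followed by an illustration of size.

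**1. The wording as logic.** Let A = plausible timing, B = no ready alternative explanation, C = resolves on stopping. *Definitely* reads (A and B) or C. *Unrelated* reads other etiology, or not A. Take not B as evidence of another etiology (an assumption, needed only for the row A yes, B no, C yes).

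| A | B | C | *Definitely* as written | *Unrelated* also fits | A and B required |
|---|---|---|---|---|---|
| no | no | no | no | yes | no |
| no | no | yes | **yes** | **yes** | no |
| no | yes | no | no | yes | no |
| no | yes | yes | **yes** | **yes** | no |
| yes | no | no | no | yes | no |
| yes | no | yes | **yes** | **yes** | no |
| yes | yes | no | yes | no | yes |
| yes | yes | yes | yes | no | yes |

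Five of eight rows reach *Definitely*. Three do so through C alone, and all three also fit *Unrelated*. Requiring A and B in every case leaves two rows and no overlap. Requiring C as well would leave one row and would shut out irreversible events.

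**2. Is this the natural reading?** In *Unrelated*, the same punctuation and conjunction join two limbs that each plainly suffice. Consistent reading gives C the same standing in *Definitely*.

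**3. Which events can reach the clause?** Only those ongoing when drug is stopped. For the planned stop, assume onset uniform over 84 days, no early stop and a fixed duration of d days. The share still open is d/84: 2/84 = 2.4%, 7/84 = 8.3%, 14/84 = 16.7%, 28/84 = 33.3%. Early stops add to this, because an event that causes discontinuation will usually be ongoing at that moment.

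**4. How often would recovery alone satisfy it?** Assume exponential durations and no drug effect. Among events open at the stop, the share resolving within w days is 1 − 2^(−w/median).

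| Window w (assumed) | Median 3 d | Median 7 d | Median 14 d |
|---|---|---|---|
| 1 day | 21% | 9% | 5% |
| 2 days | 37% | 18% | 9% |
| 3 days | 50% | 26% | 14% |
| 14 days (Day 84 to Day 98) | 96% | 75% | 50% |

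The result depends mostly on a window that the protocol does not define.

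**5. As a share of all events.** With the same durations and uniform onset, the share open at Day 84 is (m/84)(1 − e^(−84/m)), where m = median/ln 2. That is about 5%, 12% and 24% for medians of 3, 7 and 14 days. Multiplying by the 14-day row gives about 5%, 9% and 12% of all events. Multiplying by the 2-day row gives about 2% in each case.

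**The case against.** The strongest reply is that this is loose drafting with little consequence.

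- The protocol calls the grades guidelines, and *Unrelated* names intercurrent illness and underlying disease. A reader might infer that such events will be graded *Definitely*. The text permits that grade and does not compel it. This stands: the defect is ambiguity.
- The clause speaks of resolution upon stopping, and the Study Drug section gives a half-life of about 4 hours. One to two days is already 6 to 12 half-lives. A reader might infer from the 14-day row that at least half of open events qualify. That row treats any resolution by the Day 98 call as resolution upon stopping, which the text does not say, and it covers only events open at the stop. This stands.
- Known Potential Toxicity of Study Drug says that "adverse effects were generally mild to moderate and transient in nature". Events that clear during dosing never reach the clause. This stands.
- A reader might infer that the wording falsely attributes placebo events to sildenafil. Any blinded scale can call a placebo event related, so this is not specific to the clause. About 3 of 12 or 5 of 20 subjects would be on placebo.
- Section G says that hospitalization for worsening pulmonary function is not counted as an adverse event, so a hospitalized exacerbation might never be graded. This stands in part. The Adverse Events (AE) section exempts only exacerbations unrelated to study drug, so a relatedness judgment is still needed. The withdrawal rule also covers intravenous antibiotics without hospitalization.
- No planned analysis counts *Definitely* events. The Statistical analysis section looks at adverse events by arm, the definition of an adverse event ignores attribution, and the medical monitor and the DMC see serious events whatever the grade. Any error leans towards over-attribution. This stands, and it limits the harm. It does not settle which grade governs expedited reporting when an event fits both ends of the scale.

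**Conclusion.** The point holds as a defect in the causality definition. Resolution on stopping study drug satisfies *Definitely* alone, so an event ongoing at an early stop or at Day 84±3 that then resolves can fit both *Definitely* and *Unrelated*, and nothing says which prevails.

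The documents do not give the number of such events, and it is probably small in 12 to 20 subjects. The percentages above rest on assumed durations, uniform onset and an assumed window. They illustrate the dependence and do not estimate a rate. The by-arm comparison is unaffected. What is exposed is the relatedness decision behind expedited reporting and the exacerbation exemption. The documents do not support a claim that counts of definitely related events will be inflated to any stated degree.

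**What to change.** Amend the causality guidelines in the Adverse Events (AE) section and the matching CRF instructions:

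1. For *Definitely*, require plausible timing and no ready alternative explanation in every case.
2. Describe resolution on stopping as supporting evidence, neither sufficient nor required. Making it required would be a mistake: an irreversible event with plausible timing and no other cause could then not be *Definitely* and might fit no grade.
3. State that an event with evidence of another etiology is not graded *Definitely* merely because it resolved after drug was stopped.
4. Write study drug in place of sildenafil throughout the scale, since graders are blinded.

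The cost is a few lines of text. The downside is that a few events that resolve on stopping but have another explanation move to a lower grade. No dose, schedule or stopping rule changes.

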#### G. Mechanism of monitoring patient safety

*Medical Monitoring and Adverse Events:* The medical monitor will perform interim analyses of the safety data. The first interim analysis will occur after five patients have been enrolled in the study protocol. Data will be reviewed with the principal investigator on a monthly basis. Adverse events that may occur within this study population are most likely to be related to the underlying disease process as patients with cystic fibrosis are frequently hospitalized for intravenous antibiotic administration during periods of pulmonary exacerbation. Therefore, hospitalization for worsening pulmonary function will not be considered an adverse event or serious adverse event in this study protocol. However, those patients will be withdrawn from the study. Study related adverse events that will occur will most likely be related to the vasodilator effects of oral sildenafil citrate therapy. We expect the incidence of severe headache or uncomfortable symptoms of vasodilation (flushing, nasal congestion, etc.) to be self-limited.

*Serious adverse events and reporting:* Serious adverse events relating to this sildenafil therapy would include myocardial infarction, stroke, death, or anaphylactic reaction related to sildenafil citrate therapy. No patients with known cardiac disease or sildenafil allergy will be included in the study. Serious adverse events relating to exercise testing would include life-threatening arrhythmia or death during exercise testing. If any serious adverse event occurs, the principal investigator or one of the other investigators will report the incident (and any decision to suspend or halt the protocol) to the medical monitor and NJH IRB immediately (within 24 hours of becoming aware). Protocol stopping criteria will include any sildenafil citrate-related death.

*Confidentiality:* Confidentiality will be maintained through the duration of the study via strict adherence to all HIPAA compliance regulations.

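### The causality grade labelled Unlikely is defined as a reasonable possibility of relation, and no text says which grades count as related for expedited reporting

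*Combined protocol and SAP*

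**What the plan says.** The causality guidelines at the end of Adverse Events (AE) offer four grades.

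- *Definitely*: plausible timing and "the AE cannot be readily explained by the subject's clinical state, intercurrent illness, or concomitant therapies", and/or the event settles once sildenafil is stopped.
- *Probably*: plausible timing and "the AE follows a typical response to sildenafil, but a potential alternative cause may be present". Both conditions are needed.
- *Unlikely*: the definition opens with "There is a reasonable possibility that the onset of the AE is related to the administration of sildenafil" and then ranks some other explanation ahead of the drug.
- *Unrelated*: there is evidence of another cause, and/or the timing is not plausible.

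Three rules elsewhere use related or unrelated as a condition.

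- Medical Monitor: an SAE goes forward for expedited regulatory reporting if it is "classified as unexpected and related to study drug".
- Section G, Mechanism of monitoring patient safety: "Protocol stopping criteria will include any sildenafil citrate-related death".
- Adverse Events (AE), definition of a serious event: hospitalization counts, "with the exception of pulmonary exacerbation unrelated to study drug".

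None of these rules, and no other text in the protocol, says which of the four grades make an event related.

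**The concern.** A causality scale turns clinical judgement into a yes or no for regulatory reporting. Here the third grade gives the assessor two messages. Its label says that a drug effect is improbable. Its definition concedes that a drug effect is a reasonable possibility and only ranks another cause ahead of it. Two careful assessors could give the same event the same grade and still disagree on whether it is related.

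The gap matters because section G expects most adverse events to stem from the underlying disease, so a competing explanation will often be at hand. What is at stake is the expedited report of an unexpected SAE in a population in which, by the protocol's own account, the drug has not been formally studied (B. Patient Population).

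**Working it through.** No sample size, power or rate is involved, so the check is a reading of the definitions against the rules that use them.

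**Step 1. Place a test event on the scale.** Take an SAE with plausible timing that is unexpected and for which CF offers another explanation. The protocol does not define unexpected; I assume that it means not in keeping with the known effects of sildenafil.

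- *Probably* tolerates an alternative cause but requires a typical response to sildenafil. An unexpected event hardly meets that.
- *Definitely* has two routes. The first is closed, because the event can be readily explained by the subject's clinical state. The second, resolution on stopping the drug, stays open for some non-fatal events but cannot apply to a death.
- *Unrelated* needs evidence of another cause or implausible timing. A merely likelier alternative does not meet that.
- *Unlikely* is what remains, and its definition describes the event well.

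So, apart from non-fatal events that settle on withdrawal, such an event tends to be graded *Unlikely*.

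**Step 2. Apply the rules to that grade.** The documents allow two readings of related.

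| Rule | Reading A: related means any grade except *Unrelated* | Reading B: related means *Definitely* or *Probably* only |
|---|---|---|
| Expedited reporting (Medical Monitor) | Qualifies | Does not qualify |
| Sildenafil-related death criterion (section G) | Met | Not met |
| Exacerbation exception (Adverse Events) | Not exempt | Not exempt if unrelated means the grade *Unrelated*; exempt if it means not related |

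Reading B follows the label and reading A follows the definition. Nothing in the text chooses between them.

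**Step 3. Check what does not depend on the grade.**

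- Section G: any SAE is reported to the medical monitor and the IRB within 24 hours.
- Study Oversight: the DMC monitors SAEs in real time.
- Medical Monitor: all SAEs are reviewed, and the report goes to the DMC chair within one business day of that review.
- DMC: SAEs are reviewed as they arise.
- Criteria for Study Termination: the DMC may stop the study over safety concerns, and the formal safety rules are left to a DMC Charter that is not among the documents.

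Under reading B, therefore, the clear loss is the expedited regulatory report. For a death, the explicit section G criterion would also not be met, but the DMC would still see the case and could act on it.

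**The case against.** The strongest reply is that the grade is comparative: read in full, it says that a relation is conceivable but another cause is likelier. On that view *Unlikely* is a loose label and not a flat contradiction, and the Medical Monitor section does not tie its own judgement of relatedness to that label. This is fair as far as it goes. But ranking the causes does not withdraw the reasonable possibility, and the missing link between the scale and the word related is the defect itself.

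Several stronger readings are tempting, and the documents do not support them.

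- *Possibly related events escape oversight.* They do not. Every SAE reaches the medical monitor, the IRB and the DMC regardless of grade.
- *Most possible drug effects fall into this grade.* Section G expects study-related events to be mainly vasodilator effects such as flushing and congestion. Those are typical responses and fit *Probably* even when CF could explain them.
- *Dyspnea shows the problem.* Known Potential Toxicity of Study Drug lists exacerbation of dyspnea at 11% on sildenafil against 5% on placebo. As a listed effect it can be graded *Probably*, and it is hardly unexpected, so it would probably not qualify for expedited reporting under any grade.
- *Exacerbations graded Unlikely are exempt from being serious.* Read literally, the exception covers only the grade *Unrelated*. Section G separately removes hospitalization for worsening pulmonary function from adverse events with no causality condition. Renaming a grade would not alter that sentence.
- *One misgraded event distorts the arm by 11%.* With 12 subjects at 3:1, 12 × 3/4 = 9 receive sildenafil and 1/9 = 11%. If 20 is the total enrolled, 20 × 3/4 = 15 and 1/15 = 6.7%. This is the weight of one subject, not an effect of the label.
- *The trial could fail to stop after a related death.* The section G list is worded as inclusive, the DMC has discretion, and the Charter may hold further rules.

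**Conclusion.** The point holds in a limited form. The label and definition of one grade in four conflict, and related is not mapped to the scale. The consequence is a risk and not a certainty, because the protocol never says that *Unlikely* means not related. It arises for an unexpected SAE with a plausible CF explanation, when the assessor follows the label. The loss that can be shown is a missed expedited regulatory report. The death criterion and the exacerbation exception share the undefined wording, but how far they are affected cannot be settled without the DMC Charter. The documents give no figure from which to estimate how often this would happen. The change is still worth making before subjects are enrolled, because it is cheap and concerns regulatory safety reporting.

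**What to change.** 1. Rename the third grade *Possibly*, to match its definition. Alternatively, add a *Possibly* grade with that definition and redefine *Unlikely* so that it no longer concedes a reasonable possibility.
2. State in the Medical Monitor section that *Definitely*, *Probably* and *Possibly* count as related for expedited reporting.
3. Reconcile related and unrelated in section G (the death criterion and the statement on hospitalization for worsening pulmonary function) and in the Adverse Events exception with the causality grades and the DMC Charter. Which grades should trigger the stopping criterion is for the sponsor and the DMC to decide; this review does not propose a rule.

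The cost is a change to the protocol text and the CRF causality list, and slightly more events sent for expedited review.
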